10.2.3 Treatment-Emergent Adverse Events by SOC and/or PT

Treatment-emergent adverse events will be summarized by SOC and PT for the SAS-CREON-ABT and SAS-CREON-SPL; by maximum relationship to study drug as

assessed by the investigator (e.g., reasonable possibility or no reasonable possibility) and SOC and PT; by maximum severity and SOC and PT; and by subject number and SOC and PT. Specific adverse events will be counted once for each subject for calculating percentages, unless stated otherwise. In addition, if the same adverse event occurs multiple times within a subject, the highest severity and level of relationship to investigational product will be reported.

If a subject has an AE with unknown severity or relationship to study drug, the subject will be counted in the severity/relationship level category of "unknown" even if the subject has another occurrence of the same AE with a known severity/relationship. The only exception is if the subject has another occurrence of the same AE with the highest level of severity or a relationship assessment of "Reasonable possibility." In this case, the subject will be counted under the most extreme severity/relationship category.

In addition, treatment-emergent adverse events will be summarized by PT for the SAS-CREON-ABT and SAS-CREON-SPL, sorted by decreasing frequency in SAS-CREON-SPL

10.2.4 Treatment-Emergent Adverse Events per Patient-Years of Exposure

Treatment-emergent adverse events will also be summarized by PT using AE rates per 100 patient years for the SAS-CREON-ABT and SAS-CREON-SPL, sorted by decreasing rates in SAS-CREON-SPL. AE rates per 100 patient-years of exposure are defined as the number of AEs divided by the total exposure in 100 patient-years. Exposure period for CREON-ABT and CREON-SPL is the same as the reporting period for treatment-emergent AE defined in Section 10.2.1. Different occurrence of the same TEAE in a single subject will all be counted.

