5.6 Prior and Post Treatment PERT Therapy

The total daily dose of Creon® taken prior to the RIV will be recorded in the electronic case report form (eCRF).

The total daily dose of Creon® taken during the Post-Treatment 30-day Period will be recorded in the eCRF.

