APPENDIX D. ACTIVITY SCHEDULE

The following table shows the required activities across the eight subject encounters. The individual activities are described in detail in the **Operations Manual**. Allowed modifications due to COVID-19 are detailed within the Operations Manual.

Study Activities Table

Period	Screening Period	Run-in Period		Treatment Period				Post- Treatment (PT) Period
Visit Name	Screening (SCR)	Run-in Visit (RIV)	Day 1	Day 8	Day 15	Day 29	Day 85/ Premature Discontinuation (PD)	Day 115/PT Day 30
Visit Type	On-Site	On-Site	On-Site	Telemedicine	Telemedicine	Telemedicine	Telemedicine	Phone Call
□ INTERVIEWS & QUESTIONNAIRES	5							
Informed consent	✓							
Eligibility criteria	✓	✓						
Continuation criteria			✓					
Medical/surgical history	✓	✓						
Alcohol and nicotine use	✓							
Adverse event assessment	✓	✓	✓	✓	✓	✓	✓	✓
Prior/concomitant therapy	✓	✓	✓	✓	✓	✓	✓	✓
Patient reported outcome (PRO): Pancreatic Exocrine Insufficiency Questionnaire (PEI-Q)	1		V	1	*	*	✓	
Study drug usage			✓	✓	✓	✓	✓	
Dispense ePRO device			✓					
Return ePRO device (shipped after the completion of the visit)							V	
* LOCAL LABS & EXAMS								
Height (screening only) and weight	✓	✓	*					
Vital signs	✓	✓	\					
Physical examination	✓	✓	*					
Urine pregnancy test	✓	✓	✓					

Period	Screening Period	Run-in Period		Treatment Period				Post- Treatment (PT) Period
Visit Name	Screening (SCR)	Run-in Visit (RIV)	Day 1	Day 8	Day 15	Day 29	Day 85/ Premature Discontinuation (PD)	Day 115/PT Day 30
Visit Type	On-Site	On-Site	On-Site	Telemedicine	Telemedicine	Telemedicine	Telemedicine	Phone Call
* CENTRAL LABS					•			
Clinical chemistry	✓							
Hematology (complete blood count [CBC])	✓							
R _x TREATMENT								
Dispense study drug		✓	✓					
Retrieve study drug (at Day 85/PD, shipped after the completion of the visit)			*				V	
Study drug accountability (at Day 85/PD, performed after the study drug is received by the site)			V				*

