6.0 Study Drug Duration

The overall treatment duration will be summarized separately for Run-in-Period and Treatment Period. Duration of treatment is defined for each subject as (last dose date first dose date + 1). Duration of treatment will be summarized using the number of subjects treated, mean, standard deviation, median, minimum and maximum.

- 1. Summary of Duration of treatment in Run-in Period using FAS and SAS-CREON-ABT population separately. In addition, the number and percentage of subjects in each treatment duration interval 1 to <8 days of treatment, 8 to <15 days of treatment and >=15 days treatment will be summarized.
- 2. Summary of Duration of treatment in the Treatment Period using FAS population. In addition, the number and percentage of subjects in each treatment duration

interval (, 1 to \leq 8 days, 8 to \leq 15 days, 15 to \leq 29 days, 29 to \leq 85 days, \geq 85 days) will be summarized.

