10.2.1 Treatment-Emergent Adverse Events

Treatment-emergent AEs (TEAE) for the SAS-CREON-ABT are defined as any AE with the onset date on or after the first dose of the CREON-ABT until 30 days after the last dose of CREON-ABT or until the initiation of CREON-SPL, whichever is earlier. Similarly, TEAEs for SAS-CREON-SPL are defined as any AE with the onset date on or after the first dose of CREON-SPL until 30 days after the last dose of CREON-SPL. In the cases that an AE happens in a day that a subject takes both CREON-ABT and CREON-SPL, such AE will be counted under CREON-SPL. This definition will be used for all summaries except the one additional AE overview summaries in Section 10.2.2. If an incomplete onset date was collected for an AE, the AE will be assumed to be treatment-emergent unless there is evidence that confirms that the AE was not treatment-emergent (e.g., the AE end date was prior to the date of the first dose of study drug).

All TEAEs will be summarized overall, as well as by primary MedDRA SOC and Preferred Term. The SOCs will be presented in alphabetical order, and the PTs will be presented in alphabetical order within each SOC.

The number and percentage of subjects experiencing TEAEs will be summarized.

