10.2.2 Adverse Event Overview

An overview of AEs will be presented consisting of the number and percentage of subjects experiencing at least one event for each of the following AE categories for the SAS-CREON-ABT and SAS-CREON-SPL:

[figure not shown]
- Any TEAE
- TEAEs with a "reasonable possibility" of being related to study drug according to the investigator
- Severe TEAEs
- Serious TEAEs
- Serious TEAEs with a "reasonable possibility" of being related to study drug according to the investigator
- TEAEs leading to discontinuation of study drug
- TEAEs leading to death
- TEAEs of Special Interest
- TEAEs of Special Interest with a "reasonable possibility" of being related to study drug according to the investigator
- All deaths

The same summaries will be repeated by restricting the analysis period of SAS-CREON-ABT and SAS-CREON-SPL to 28 days after the first dose of CREON-ABT and CREON-SPL, respectively. For SAS-CREON-ABT, the analysis period will not include days on or after the first dose of SAS-CREON-SPL.

The same summaries will also be repeated by using AE rates per 100 patient years of exposure, instead of number and percentage of AEs. For this summary, the definitions of SAS-CREON-ABT and SAS-CREON-SPL in Section 10.2.1 will apply.

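### The AE rates per 100 patient-years count 30 days after CREON-SPL has stopped as CREON-SPL exposure, but add no such tail to CREON-ABT for subjects who switch

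*SAP*

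**What the plan says.** SAP 10.2.4 plans AE rates per 100 patient-years by preferred term for both products, counting every occurrence and sorting by the CREON-SPL rate. The denominator is defined as follows: "Exposure period for CREON-ABT and CREON-SPL is the same as the reporting period for treatment-emergent AE defined in Section 10.2.1".

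SAP 10.2.1 sets those reporting periods:

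- **CREON-SPL:** onset "on or after the first dose of CREON-SPL until 30 days after the last dose of CREON-SPL".
- **CREON-ABT:** from the first dose to 30 days after the last dose "or until the initiation of CREON-SPL, whichever is earlier".

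SAP 10.2.2 applies the same windows to the AE overview: "The same summaries will also be repeated by using AE rates per 100 patient years of exposure". It also plans a restricted version of the overview: "The same summaries will be repeated by restricting the analysis period of SAS-CREON-ABT and SAS-CREON-SPL to 28 days after the first dose" of each product.

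SAP 6.0 measures time on drug differently. "Duration of treatment is defined for each subject as" last dose date minus first dose date plus one, with no tail.

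Two protocol entries describe the 30 days after CREON-SPL. Appendix D lists the activity "Retrieve study drug (at Day 85/PD, shipped after the completion of the visit". Section 5.6 says that the total daily dose of Creon "taken during the Post-Treatment 30-day Period will be recorded in the eCRF".

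**The concern.** The rate labelled CREON-SPL exposure combines two kinds of time: about 85 days on CREON-SPL, and 30 days after it has stopped and the study supply is being returned. Protocol 5.6 expects Creon use in those 30 days and records it separately. The tail is therefore expected to be time on Creon from outside the study supply. A switcher's CREON-ABT time has no such tail, and only subjects who never start CREON-SPL add one to CREON-ABT.

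The study exists to describe symptoms after a change of ingredient source, and its AESIs are EPI symptoms, so it matters which product a day is credited to. The rates are also the only planned AE summary that allows for unequal follow-up (28 against 85 days) over the whole period and by preferred term. If the tail behaves like CREON-ABT time, a real difference between the products in either direction is pulled towards a ratio of 1.

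**Working it through.** **Inputs.** Screening up to 14 days and run-in 28 days (protocol 4.1, SAP 2.2); CREON-SPL 85 days (SAP 2.3); follow-up 30 days (protocol 4.1, SAP 2.2); about 30 enrolled, 20% dropout, about 24 evaluable (protocol 7.7, SAP 2.4). A year is taken as 365.25 days.

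**Check of the period lengths.** 14 + 28 + 85 + 30 = 157 days, which matches the maximum participation of approximately 157 days in protocol 4.1. The documents state no AE rate or patient-year total to reproduce.

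**Person-time under SAP 10.2.4**

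- CREON-SPL completer: 85 + 30 = 115 days; tail share 30/115 = 26.1%. Taking dosing as 84 days gives 30/114 = 26.3%.
- CREON-ABT, subject who switches: 28 days; tail share 0%.
- 24 CREON-SPL completers: 24 × 115/365.25 = 7.56 patient-years counted, of which 24 × 85/365.25 = 5.59 are on drug and 24 × 30/365.25 = 1.97 are tail.
- Early stopping changes little. If 2 of 24 stop at Day 29, the tail share is 720/(22 × 85 + 2 × 29 + 720) = 720/2648 = 27.2%.

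**Effect on the CREON-SPL rate.** Let q = AE rate in the tail / AE rate on CREON-SPL. Tail events are in the numerator, so reported rate / on-drug rate = (85 + 30q)/115. The documents do not give q; the range below is assumed.

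| q | reported / on-drug |
|---|---|
| 0 | 85/115 = 0.74 |
| 0.5 | 100/115 = 0.87 |
| 1 | 115/115 = 1.00 |
| 1.25 | 122.5/115 = 1.07 |

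**Effect on the two products side by side, if the tail rate equals the CREON-ABT rate.** This is an assumption. Let k be the on-drug CREON-SPL:CREON-ABT rate ratio. With no CREON-ABT tail, the reported ratio is (85k + 30)/115.

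| k | reported ratio |
|---|---|
| 0.7 | 89.5/115 = 0.78 |
| 1 | 115/115 = 1.00 |
| 1.5 | 157.5/115 = 1.37 |
| 2 | 200/115 = 1.74 |

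**Allowing for CREON-ABT tails.** Suppose m of 30 subjects never start CREON-SPL, each stopping after the full 28 days and adding 30 days. The CREON-ABT tail share is 30m/(840 + 30m). With the same q in both tails, the reported ratio is the on-drug ratio multiplied by [(85 + 30q)/115] / [(840 + 30mq)/(840 + 30m)].

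| m | CREON-ABT tail share | factor, q = 0 | factor, q = 0.5 |
|---|---|---|---|
| 0 | 0% | 0.74 | 0.87 |
| 3 | 90/930 = 9.7% | 0.82 | 0.91 |
| 6 | 180/1020 = 17.6% | 0.90 | 0.95 |

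Here m = 6 is the whole planned 20% dropout falling before Day 1.

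**What the 28-day overview covers.** It repeats the overview categories, including AESIs, as numbers and percentages over a similar early window for each product. It gives no rates by preferred term and stops before Days 29–85, which are 57 of 85 dosing days (67%).

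**The case against.** The definition is disclosed and uses one window for numerator and denominator, so the result is a valid rate for the reporting period. The same rule applies to both products; the asymmetry comes from the fixed order of CREON-ABT then CREON-SPL. Bias is not demonstrated, because q is unknown. The 0.74 extreme needs no AE at all in the tail, which is hard to square with patients still taking Creon, so a q nearer 1 is more natural. The documents also do not state which ingredient source the post-treatment Creon has.

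The study is descriptive, plans no ratio or interval between products, and already has the 28-day overview. Event numbers will be small: with an assumed 5 CREON-ABT and 15 CREON-SPL events, the log standard error of the rate ratio is √(1/5 + 1/15) = 0.52, a 95% interval of about ×/÷ 2.75. On-drug rates would still be confounded by period order and by the Day 1 continuation criteria, and a cutoff at last dose drops events that start just after stopping.

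Much of this stands. The direction is unknown, no test or endpoint depends on the rates, random error will exceed the shift in most rows, and the remedy does not make the periods fully comparable. It does not remove the point. The table calls the tail product exposure and sets it beside a CREON-ABT rate with little or no tail. Small numbers do not justify crediting events to a product that has stopped, and the 28-day overview leaves the preferred-term rates and two thirds of CREON-SPL dosing without an on-drug version. Late-onset events are kept if they are shown separately.

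**Conclusion.** The concern holds. Under SAP 10.2.4, 26% of a completer's CREON-SPL person-time, and any events in it, fall after CREON-SPL has stopped; subjects who switch contribute no such time to CREON-ABT. That share follows directly from the stated period lengths.

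The effect on the rates rests on assumptions. The CREON-SPL rate could read 26% too low if the tail has no events, correct if the tail rate equals the on-drug rate, or too high if the tail rate is larger. If the two products and the tail share one rate, nothing changes. CREON-ABT tails from subjects who never switch narrow the discrepancy but do not close it, even if all six planned dropouts fall before Day 1, unless q = 1. This is a labelling and comparability weakness in descriptive safety tables. It is worth correcting, but it affects no hypothesis test, sample size or pharmacodynamic result.

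**What to change.** In SAP 10.2.4 and in the rate version of the SAP 10.2.2 overview:

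1. Add rates in which events and person-time are both limited to time on each product, from first to last dose as in SAP 6.0. End CREON-ABT before the first CREON-SPL dose, consistent with the same-day rule in SAP 10.2.1.
2. Name these as the rates to use when CREON-SPL is read against CREON-ABT.
3. Show post-treatment events and person-time in a separate column.
4. Keep the 30-day window for the number-and-percentage tables of TEAEs, SAEs and deaths, and keep the currently planned rates as a supplement.

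The cost is a change of SAP wording and one date cutoff, since SAP 6.0 already uses the first and last dose dates. No late-onset event is lost. The downside is one extra set of rate columns.

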5.7 Withdrawal of Subjects and Discontinuation of Study

A subject may voluntarily withdraw or be withdrawn from the study at any time for reasons including, but not limited to, the following:

- The subject requests to be withdrawn from the study.
- Any intake of pancreatic enzyme preparations in addition or substitution to the study drug during the study.
- When continuation of the study drug would place the subject at risk, as determined by the Investigator.
- Subjects who become pregnant during the study.
- Subject is significantly noncompliant with study procedures, which would put the subject at risk for continued participation in the study.
- Subject does not meet all continuation criteria at Day 1.

For subjects to be considered lost to follow-up, reasonable attempts must be made to obtain information on the subject's final status. At a minimum, 2 telephone calls must be made and 1 certified letter must be sent and documented in the subject's source documentation.

AbbVie may terminate this study prematurely, either in its entirety or at any site. The investigator may also stop the study at his/her site if he/she has safety concerns. If AbbVie terminates the study for safety reasons, AbbVie will promptly notify the investigator.

COVID-19 Pandemic-Related Acceptable Protocol Modification

During the COVID 19 pandemic, it may be necessary to employ mitigation strategies to enable the investigator to ensure subject safety and continuity of care. Refer to Section 2 and Section 3.1 of the Operations Manual in Appendix E.

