5.8 Follow-Up After Subject Discontinuation of Study Drug or from Study

To minimize missing data for study assessments, subjects who prematurely discontinue study drug treatment should continue to be followed for all regularly scheduled visits, unless subjects have decided to discontinue the study participation entirely (withdrawal of informed consent). Subjects should be advised on the continued scientific importance of their data even if they discontinue treatment with study drug early.

If a subject prematurely discontinues study participation (withdrawal of informed consent), the procedures outlined for the Premature Discontinuation Visit (PD Visit) should be completed as soon as possible, preferably within 2 weeks. In addition, if subject is willing, a 30-day follow-up phone call after the last dose of study drug may be completed to ensure all treatment-emergent AEs/serious adverse events (SAEs) have been resolved.

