7.7 Sample Size Determination

Approximately 30 subjects will be enrolled at the RIV. The sample size is calculated based on the descriptive statistics for the TSS based on PEI-Q. No formal statistical hypothesis testing is planned. Assuming a dropout rate of 20% after the RIV, the number of evaluable subjects will be around 24 for the analysis of pharmacodynamic endpoints.

Based on Johnson CD, et al,⁶ the average TSS from PEI-Q was estimated to be 1.4 (SD = 0.7) for CP and CF subjects with EPI symptoms. Assuming the covariance between the TSS at baseline and post-baseline after switching to **CREON-SPL** to be 0.365, the SD for the change of the TSS between baseline and post-baseline is estimated to be 0.5. A sample size of 24 evaluable subjects will provide a precision of \pm 0.2 in terms of half-length of the 95% confidence interval for the estimate of change in TSS based on PEI-Q.

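### The patient-year denominator does not stop at death or at the last adverse-event contact, so subjects who leave before CREON-SPL can add up to 30 unobserved days each and lower the CREON-ABT rate

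*SAP*

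**What the plan says.** SAP 10.2.4 defines the rate: "AE rates per 100 patient-years of exposure are defined as the number of AEs divided by the total exposure in 100 patient-years". It then fixes the denominator: "Exposure period for CREON-ABT and CREON-SPL is the same as the reporting period for treatment-emergent AE defined in Section 10.2.1".

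SAP 10.2.1 supplies the two windows. For CREON-ABT the window opens at the first dose and lasts "until 30 days after the last dose of CREON-ABT or until the initiation of CREON-SPL, whichever is earlier". For CREON-SPL it covers onsets "on or after the first dose of CREON-SPL until 30 days after the last dose of CREON-SPL". Neither section names death, withdrawal from the study or last contact as an end point.

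SAP 10.2.2 uses the same denominator for the AE overview: "The same summaries will also be repeated by using AE rates per 100 patient years of exposure".

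On follow-up, Protocol 6.1 plans AE collection to 30 days after study drug is stopped. Protocol 5.8 keeps subjects who only stop drug in the visit schedule. After withdrawal of consent it asks for a Premature Discontinuation (PD) visit, preferably within two weeks, and adds: "if subject is willing, a 30-day follow-up phone call after the last dose of study drug may be completed". Protocol 5.7 provides for loss to follow-up: "For subjects to be considered lost to follow-up, reasonable attempts must be made to obtain information on the subject's final status". The Post-Treatment Period text in Protocol 4.1 gives the 30-day telephone follow-up to subjects who finish or stop the Treatment Period. It does not name those who leave in the run-in or fail the continuation criteria at Day 1.

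**The concern.** Person-time should count only days on which an event could have become known. The SAP's rule is a calendar window, so a programmer who follows it credits 30 post-dose days to a subject who died or was never reached again. Those days can add nothing to the numerator, and the rate falls.

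The effect differs between the two products. For a subject who switches, the CREON-ABT window closes at the switch. Post-dose CREON-ABT days therefore come only from subjects who never start CREON-SPL. Such exits are foreseen: failing a continuation criterion is a listed reason for withdrawal (Protocol 5.7), and SAP 5.0 tabulates it. Thirty extra days also weigh more against a 28-day period than against about 115 days. If leavers before the switch go uncontacted, two identical products would show a higher AE rate on CREON-SPL. The rate tables are one of the SAP's two ways of setting periods of unequal length side by side, so a distortion there matters to the reader.

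**Working it through.** **Inputs.** 30 enrolled and 20% dropout after the Run-in Visit (Protocol 7.7: "Assuming a dropout rate of 20% after the RIV"); 28 days of CREON-ABT and 85 days of CREON-SPL (SAP 2.3); a 30-day tail (SAP 10.2.1).

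**The plan's own figures.** 30 × (1 − 0.20) = 24 evaluable, as stated. 14 + 28 + 85 + 30 = 157 days, the stated maximum participation. A CREON-SPL completer's window is 85 + 30 = 115 days and ends with the scheduled Day 115 call, so it is observed when that call is made.

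**CREON-ABT.** Let m be the number of subjects who never start CREON-SPL, d their days on CREON-ABT, and k the post-dose days (of 30) actually observed.

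- Counted days = (30 − m) × 28 + m × (d + 30)
- Observed days = (30 − m) × 28 + m × (d + k)
- Understatement of the rate = 1 − observed/counted = m × (30 − k)/counted

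| m | d | Counted days | k = 0 | k = 14 | k = 30 |
|---|---|---|---|---|---|
| 1 | 28 | 29×28 + 58 = 870 | 3.4% | 1.8% | 0% |
| 1 | 1 | 29×28 + 31 = 843 | 3.6% | 1.9% | 0% |
| 3 | 28 | 27×28 + 3×58 = 930 | 9.7% | 5.2% | 0% |
| 3 | 1 | 27×28 + 3×31 = 849 | 10.6% | 5.7% | 0% |
| 6 | 28 | 24×28 + 6×58 = 1020 | 17.6% | 9.4% | 0% |
| 6 | 1 | 24×28 + 6×31 = 858 | 21.0% | 11.2% | 0% |

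The k = 14 column stands for a PD visit two weeks after the last dose with nothing later. For m = 6, d = 28, k = 0, observed time is 840 days. If CREON-SPL is fully observed, a true rate ratio of 1 would appear as 1020/840 = 1.21. If only three of those six go uncontacted and the rest are fully followed, the understatement is 90/1020 = 8.8%.

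**CREON-SPL.** With 24 starters, of whom m stop at day d, counted days = (24 − m) × 115 + m × (d + 30). For one uncontacted subject stopping at day 42: 23×115 + 72 = 2717 days, and 30/2717 = 1.1%. For d from 1 to 85, three such subjects give 3.3-3.6% and six give 6.5-8.0%.

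Per lost subject, the relative effect on CREON-ABT is about three times that on CREON-SPL.

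**The case against.** **The tail is planned observation.** AE collection runs to 30 days after stopping, subjects who only stop drug stay in the schedule, and the PD visit after withdrawal of consent includes an AE assessment. Subjects who fail the continuation criteria are seen on site that day and need not be unreachable. This stands: days are unobserved only where the plan fails or is silent, and the error is zero if follow-up is complete. It does not remove the defect, because the call after withdrawal of consent is optional, run-in leavers are not named in the Post-Treatment Period text, and no follow-up plan covers death.

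**Little depends on these tables.** The study is descriptive and no decision uses the rates. SAP 10.2.2 also repeats the overview over 28 days from the first dose of each product, a matched comparison that does not use this denominator. Sampling error is far larger: 840 days is about 2.3 patient-years, and if 10 events occurred (an assumed count) the exact Poisson 95% interval would run from about 52% below to 84% above the estimate. This also stands and limits the weight of the point. Sampling error is, however, shown by small counts, whereas this shift is invisible to the reader.

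**Stronger readings.** A reader might infer that the denominator always runs 30 days past the last dose. That would give 30 × 58 = 1740 CREON-ABT days against 840 and a rate 52% too low. The cut-off at the first CREON-SPL dose rules this out. A reader might also take 10-20% as the expected error. That needs about 3 to 6 leavers before CREON-SPL with essentially no post-dose day observed, which the documents do not say.

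**Conclusion.** The concern holds as a defect in a stated rule: the exposure window has no stop at the end of observation, so unobserved days can enter the denominator of the per-100-patient-year tables in SAP 10.2.2 and 10.2.4. Subject percentages and the 28-day overview are unaffected.

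Assuming 3 to 6 of 30 subjects leave before CREON-SPL, the CREON-ABT rate is understated as follows:

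- 0% with complete follow-up;
- about 5-9% if leavers finish the 28 days and 14 of the 30 post-dose days are observed, or up to 11% if they leave sooner;
- about 10-21% if no post-dose day is observed.

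The documents give neither the timing of dropout nor the number of uncontacted leavers, so this is a range and not a forecast. For the same reason, that most unobserved days would fall on CREON-ABT cannot be shown. What can be shown is the larger relative effect per lost subject (about 3.5% against 1.1%). The direction also depends on who is lost: losses before the switch make CREON-SPL look worse, while losses during CREON-SPL lower its own rate by less.

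**What to change.** In SAP 10.2.4, and for the rate version of the overview in 10.2.2, define each subject's person-time as running from the first dose of the product to the earliest of:

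- the end of the 10.2.1 window;
- death;
- the last date on which AE status is known, meaning the last AE assessment (including a PD visit) or a later AE report.

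Withdrawal from the study need not be a separate stop, since a PD visit or later report may still give AE information after it. Leave the TEAE definition and all other tables as they are. List any TEAE with onset after the person-time end date, so that a collected event is not lost when the rate table is restricted.

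Cost: one sentence in the SAP and one extra derived date per subject and product. AE assessment is scheduled at every encounter in the Activity Schedule, so the dates should be available. CREON-ABT patient-years become slightly fewer and the CREON-ABT rate slightly higher. If every planned contact takes place, the results do not change.
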